8.0 Pretreatment Evaluation

- 8.1 A history and physical, including detailed neurological exam and recording of Karnofsky Performance Status (KPS) will be performed on all patients enrolled.
- 8.2 Patients will be referred for a detailed neuropsychological evaluation by the neuropsychology team. Neuropsychological evaluation will include the battery of standardized tests and measures listed below which will comprise the primary instruments of interest for the purposes of this study. This standardized battery is routinely used to assess patients with intracranial tumors at MDACC. The following tests were selected because they are widely used, standardized psychometric instruments that have been shown to be sensitive to the neurotoxic effects of cancer treatment in other clinical trials [19, 43, 44]. Normative data have been published for all tests that take into account age, education and sex, where appropriate. These tests were also selected to minimize practice effects on repeated administration. The memory test has six alternate forms and the verbal fluency test has two alternate forms. Additional tests and measures will be administered to patients at the discretion of the attending neuropsychologist based on clinical need for each individual patient. The neuropsychological evaluation will take approximately 2 hours of face-to-face contact with the patient to complete all of the testing. All reasonable effort will be made to complete testing prior to the start of radiation therapy. However, in cases where this is not possible evaluation will be completed within the first 5 fractions of radiation treatment.

Cognitive Function Measured	Test
Memory	Hopkins Verbal Learning Test-Revised[45]
Psychomotor Speed	Trail Making Test Part A[46]
Executive Function	Trail Making Test Part B [46]
Executive Function	Controlled Oral Word Association[47]
Symptom/QOL Measures	Test
Symptom	MD Anderson Symptom Inventory Brain Tumor (MDASI-BT) [48]
Quality of Life	EORTC QLQ C30/BN20 [49]

- 8.3 Laboratory studies including CBC, liver function tests including AST, ALT, alkaline phosphatase, electrolytes, and Blood Urea Nitrogen (BUN)/Serum creatinine.
- 8.4 Routine MRI of the brain with and without contrast and including diffusion weighted images must be obtained prior to initiation of radiation and no greater than 4 weeks prior to study registration and reviewed by radiology to identify all measurable disease. This scan will be considered the baseline scan (time 0).

9.0 Evaluation During Study

- 9.1 A history and physical exam will be performed at two month intervals for a total of 24 months of follow up after the completion of the assigned treatment (±30 days). Note the first evaluation after radiotherapy will frequently be performed approximately 4 weeks after completion of radiotherapy and then the study will continue with history and physical exam at 2 month intervals.
- 9.2 Neuropsychological testing will be performed at each follow up visit, up to two years post radiation treatment. Reasonable effort will be made to complete this testing prior to patients meeting with their physicians and receiving information about the status of their disease.
- 9.3 Routine MR imaging of the brain performed with and without contrast will be obtained at each follow up visit at 2 month intervals (±30 days) until recurrence or up to two years post radiation treatment. Note the first evaluation after radiotherapy will frequently be performed approximately 4 weeks after completion of radiotherapy and then the study would continue with follow-up imaging at 2 month intervals. These post-treatment scans will be analyzed and compared to baseline scans for identification of regions demonstrating changes in contrast enhancement including size, heterogeneity and rim thickness. Qualitative estimation of associated T2-FLAIR changes will also be evaluated. Early stages of malignant gliomas have demonstrated decreased water diffusion. Routinely obtained diffusion weighted images and reconstructed ADC maps will be analyzed to see if there is a difference between pre- and various post-treatment scans. Based on contrast enhancing imaging features, manually selected regions of interest on ADC maps will be

quantitatively analyzed, normalized to contralateral unaffected brain parenchyma and compared on serial scans. Similarly DTI maps and cognitive functions will be correlated.

- 9.4 Medication usage (specifically steroid dose, narcotic pain medications, antiepileptic agents, psychostimulants) will be recorded. Steroid doses will be adjusted based on clinical and radiographic criteria.
- 9.5 Requirements for more frequent evaluation will be documented. Data on unscheduled follow-ups will also be documented.
- 9.6 Research blood products will be collected within the first five fractions of treatment and at each evaluation period as stated above. At each interval, 2 tubes (10 mL) of serum (using "red" top tube, no additive) and 1 tube (10 mL) of whole blood (EDTA additive, "purple" top tube) will be collected.

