10.2.1.3 Progressive Disease (PD): Defined as any of the following 1) \geq 25% increase in the sum of the products of perpendicular diameters of enhancing lesions compared with the smallest tumor measurement obtained either at baseline (if no decrease) or best response, on stable or increasing dose of corticosteroids; 2) significant increase in T2/FLAIR nonenhancing lesion on stable or increasing doses of corticosteroids compared with baseline or best response not caused by comorbid events (i.e. radiation therapy. demvelination, ischemic injury postoperative changes); 3) any new lesion; 4) clear clinical deterioration not attributable to other causes apart from tumor (i.e. seizures, medication adverse effects, complications of therapy, cerebrovascular events, infection, or decrease in corticosteroid dose); 5) failure to return for evaluation due to death or deteriorating condition; 6) clear progression of non-measurable disease.

When making the diagnosis of progressive disease it is import to recognize the possibility of pseudo-progression, especially if the patient is clinically stable. In those situations, treatment should continue and status of local control should be evaluated with a repeat interval scan. If the subsequent scan confirms progression then the date of progression should be backdated to the original scan suggesting progression.

- 10.2.1.4 Stable Disease (SD): Requires all of the following 1) does not qualify for complete response, partial response, or progression; 2) stable FLAIR/T2 lesions on corticosteroid dose no greater than at baseline; 3) clinical status stable.
- 10.2.1.5 For local control, PD is considered local failure, or stable disease with deterioration of the neurological examination with a grade III or worse toxicity on the CTCAE v.4.0 scale (see Appendix). All others (CR, PR, asymptomatic SD) are deemed success.
- 10.2.2 Overall survival will be measured from registration until death. After 2 years of follow-up event monitoring will be used.
 - 10.2.2.1 Patients with unknown vital status will be censored at the date of last visit or MRI scan.
- 10.2.3 Quality of life will be measured at each two month interval follow up visit out to two years using the EORTC QLQ C30/BN20 and the MD Anderson Symptom Inventory Brain Tumor (MDASI-BT).

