12.0 Statistical Considerations

- 12.1 Randomization procedure: A stratified block randomization procedure will be used. Randomization will be performed using CORe. The randomization strata are as defined above in section 7.0, and the block size will be 6. Patients who withdraw from the study after randomization, but prior to receiving treatment will be considered a cancel and replaced.
- 12.2 Sample size: With IMRT the cognitive function failure rate at 4 months is 45%, based off of comparative analyses of the cognitive failure rate of RTOG 0614 and compared to the cognitive impairment seen on RTOG 0525; we hope to demonstrate that IMPT can achieve a cognitive function failure rate at 4 months of only 30%. We assume the time to cognitive failure in each treatment arm follows an exponential distribution. A cognitive failure rate of 45% at 4 months then implies a median time to cognitive failure of 4.6 months, while a cognitive failure rate of 30% at 4 months implies a median time to cognitive failure to cognitive failure of 7.8 months.

We will use a 1-sided significance level of 0.20 as suggested by Rubinstein et al. [51]for phase II screening trials. We expect to enroll 2 patients per month, and we will randomize 60 evaluable patients (30 to each treatment arm). We will have 80% power to detect an improvement in cognitive failure at 4 months from 45% in the IMRT arm to 30% in the IMPT arm. We expect to observe 43 events, and the analysis will be performed once we have observed these events. We define evaluable patients as those who have received the assigned treatment *and* completed baseline and at least one follow-up neurocognitive testing. We expect we will need an over accrual of 33% to account for those patients not evaluable. Therefore the target total enrollment sample size is 90 patients to accrue a total of 60 evaluable patients. We expect to observe 43 events, and we expect the trial to take 41 months to observe these events.

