13.0 Data and Protocol Management

13.1 To ensure protocol compliance, the principal investigator, treating radiation oncologist, study neuroradiologist and research nurse will review the patient data and MRI films prior to randomization. All required pretreatment data

should be available before a decision to enroll the patient on the protocol is made.

- 13.2 All data with the exception of the neuropsychological data will be collected by the research nurse in charge of the protocol. This includes pretreatment, treatment, and post treatment data. The neuropsychological data will be collected by members of the Section of Neuropsychology. [name] will maintain a study specific database containing the cognitive outcomes. The medical and neuropsychological databases will be integrated by the study statistician at the time of analysis and/or to prepare for MDACC DSMB review. The study chairman will act as the final arbitrator of all study parameters should a difference of opinion exist. Patients who meet eligibility criteria will be registered in CORe.
- 13.3 De-identified DICOM images and matched clinical variables will be shared with [name], PhD, University of Texas at Austin, Biomedical Engineering, TX, US; using secured M.D. Anderson Box cloud. The purpose of this collaboration is to spearhead an effort to leverage advanced imaging modalities, including multi-parametric and functional MRI to identify clinically applicable non-invasive means of characterizing radiation-induced normal brain injury and subsequent prediction of patterns of cognitive side effects.
- 13.4 De-identified DICOM images and matched clinical variables will be shared with [name], PhD, University of Michigan, Department of Computational Medicine & Bioinformatics; using secured M.D. Anderson Box cloud. The purpose of this collaboration is to spearhead an effort to leverage advanced imaging modalities, including longitudinal multi-parametric and functional MRI to identify clinically applicable non-invasive means of characterizing patterns of tumor response to radiation treatment.

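### The plan does not keep the treatment arm from those who give and score the primary cognitive tests or judge progression, and the baseline test may follow allocation

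*Combined protocol and SAP*

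**What the plan says.** **Follow-up testing.** Section 9.2 says "Reasonable effort will be made to complete this testing prior to patients meeting with their physicians" and hearing about their disease. Treatment arm is not mentioned.

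**Baseline testing.** Section 8.2 aims for the battery to be done before radiotherapy starts, then adds: "However, in cases where this is not possible evaluation will be completed within the first 5 fractions of radiation treatment". Section 7.2 has insurance authorization sought for the assigned modality after randomization, so by fraction 1 the patient knows the arm. Section 13.1 says that all required pretreatment data "should be available before a decision to enroll the patient on the protocol is made".

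**Progression.** Sections 10.1.1 and 12.3 make progressive disease a competing event in the primary analysis. Among the criteria in 10.2.1.3 is "clear clinical deterioration not attributable to other causes apart from tumor". That section also asks for a judgement on significant T2/FLAIR change and on possible pseudo-progression.

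**Who collects and decides.** Section 13.2 gives cognitive data collection to the Section of Neuropsychology, with its own database. It also states: "The study chairman will act as the final arbitrator of all study parameters should a difference of opinion exist".

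**Masking.** None is planned for any of these people. The only blinding mentioned in the document concerns the past validation cohort of the prognostic classifier in 5.2.4.

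**The concern.** Patients and treating physicians cannot practicably be masked to protons versus photons, but outcome assessors can. The cognitive battery is part of a face-to-face examination of about two hours (8.2), and a decline on any one of six variables counts as failure. Every reliable-change decision is measured from the baseline score. If that score is obtained after allocation, expectation can enter the reference as well as the follow-up.

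A second route runs through progression. If progression is declared first, a later cognitive decline no longer counts as an event of interest. A difference between arms in how readily deterioration is attributed to tumor would therefore change the primary comparison.

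Section 4.0 states the hypothesis that IMPT gives better cognitive outcomes. The trial is small and its test is lenient by design ("We will use a 1-sided significance level of 0.20"), so a few reclassified patients could matter.

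**Working it through.** **Inputs (Section 12.2).** One-sided alpha 0.20; power 80%; 4-month failure 45% on IMRT and 30% on IMPT; exponential times; 60 evaluable patients, 30 per arm; 43 events.

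**Step 1: reproduce the plan.** The design hazard ratio is ln 0.70 / ln 0.55 = 0.597. With z = 0.8416 for both alpha 0.20 and power 0.80, the Schoenfeld formula gives 4 × (0.8416 + 0.8416)² / (ln 0.597)² = 11.333 / 0.2668 = 42.5, so 43 events, as stated. Power at 43 events is Φ(0.5165 × √43 / 2 − 0.8416) = Φ(0.852) = 0.80, which agrees with the plan. The design arithmetic is sound and is not in question.

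**Step 2: what counts as positive.** The critical hazard ratio is exp(−2 × 0.8416 / √43) = 0.774. Against 45% on IMRT this is 1 − 0.55^0.774 = 37% on IMPT. The gap of 8 points is 0.08 × 30 = 2.4 patients.

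**Step 3: no true effect, a few patients scored differently.** Suppose k fewer of the 30 IMPT patients are scored as failed by 4 months. Then p = 0.45 − k/30, HR = ln(1 − p) / ln 0.55, and P(positive) = Φ(−ln HR × √43 / 2 − 0.8416).

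| k | p | Apparent HR | P(positive), alpha 0.20 | Same shift, alpha 0.025 |
|---|---|---|---|---|
| 0 | 0.450 | 1.00 | 0.20 | 0.025 |
| 1 | 0.417 | 0.90 | 0.31 | 0.05 |
| 2 | 0.383 | 0.81 | 0.44 | 0.10 |
| 3 | 0.350 | 0.72 | 0.59 | 0.19 |

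A cruder comparison of two proportions at 4 months, 30 per arm, gives 0.28, 0.375 and 0.48 for k = 1, 2 and 3. Like the plan's own sample size, the table ignores competing risks and treats the shift as a constant hazard ratio.

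**Step 4: shift in test scores.** Assume six equally correlated normal change scores (correlation 0.3 to 0.7) and a common cut-off that gives 45% any-of-six failure. Shift the IMPT scores favourably by 0.1 to 0.3 SD of the change score and convert to P(positive) as in step 3.

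| Shift | One of six variables | All six, every IMPT patient |
|---|---|---|
| 0.1 SD | 0.22 | 0.35–0.38 |
| 0.2 SD | 0.23–0.24 | 0.52–0.59 |
| 0.3 SD | 0.25–0.26 | 0.71–0.79 |

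The documents give no bias size and no correlation between tests; both are assumptions.

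**Step 5: baseline timing.** Section 8.2 ties baseline to the start of radiotherapy, with a fallback to fraction 5, and does not tie it to randomization. Section 13.1 asks for required pretreatment data before the decision to enrol. The battery sits under the heading Pretreatment Evaluation. If it is part of the required data, 13.1 puts baseline before randomization and 8.2 permits it afterwards. If it is not, the two sections agree. The text does not say which is meant.

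**The case against.** The strongest reply is that much already limits tester influence. The battery is standardized with published norms, six memory forms and two fluency forms, and failure is a numeric reliable-change threshold and not a rating. Progression also has firmer criteria: a 25% measured increase, any new lesion, and a repeat scan where pseudo-progression is suspected. This stands. It narrows the route without closing it.

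A reader might infer that the testers and those who call progression do know the arm, or that the tests are scored by hand. The documents say neither. They do not name the progression reader or describe scoring. What they support is that nothing prevents these people from knowing the arm. Nor is a firm contradiction between 8.2 and 13.1 shown; it depends on what 13.1 means by required data.

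The larger percentages in step 4 also need care. A 0.3 SD shift on all six variables lowers IMPT failure to about 30–32%, close to the design alternative of 30%, so a rejection rate of 0.71–0.79 largely restates the planned power ("We will have 80% power to detect an improvement in cognitive failure at 4 months"). A late-baseline effect would touch only those tested late. The primary analysis in 12.3 also counts non-evaluable patients as failures. Adding 30 such failures spread evenly over the arms at time zero (an assumed timing) reduces the all-six figures from about 0.37, 0.55 and 0.74 to 0.34, 0.48 and 0.64. The all-six row is therefore an upper-end scenario.

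Finally, late baselines and progression calls could bias the result in either direction. The calculations show only shifts that favour IMPT.

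**Conclusion.** The point holds as a gap in the design. As written, the plan leaves an avoidable route by which knowledge of the arm can reach the primary result, through test administration and scoring, through a baseline done after allocation, and through the competing event. Sections 8.2 and 13.1 should be reconciled.

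One to three patients of 30 scored differently would move the false-positive probability from 0.20 to about 0.31–0.59. A 0.1–0.3 SD shift would move it to 0.22–0.26 if one variable is affected, and to 0.35–0.79 if all six are affected in every IMPT patient. These figures rest on no true effect, 43 events, a constant apparent hazard ratio and assumed bias sizes.

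It would be tempting to conclude that a positive result from this trial would be an artefact. The documents do not support that: they contain no evidence that bias occurs, how large it is, or which arm it favours.

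**What to change.** 1. **Section 8.2:** complete the baseline battery before the allocation is released, and word 13.1 to match. For any patient tested later, record the timing by arm and repeat the primary analysis without those patients.
2. **Sections 9.2 and 13.2:** withhold the arm from the neuropsychology staff who administer and score the tests, and compute reliable-change status by program from raw scores.
3. **Sections 10.2.1 and 13.2:** have the existing study neuroradiologist read the serial MRIs for RANO without the arm, and settle any dispute over progression or cognitive failure on a file with the arm removed.
4. **Report:** state that patients were unmasked.

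**Cost.** The 43 events, 60 evaluable patients and 90 enrolled are unchanged. A separate neuropsychology section and a study neuroradiologist already exist, although the databases are also merged for DSMB review, so the merged file should not reach the testers. Baseline scheduling becomes tighter. Some unmasking will occur, through patients or because the neuropsychologist also has a clinical role (8.2). Only part of any expectation effect is removed.

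The protocol is Version 15 of March 2019 and does not state accrual status. If accrual has ended, baseline timing can no longer be changed, but the analysis without late baselines and a masked re-reading of the MRIs remain possible.

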10.0 Criteria for Response and Toxicity

10.1 Definition of primary endpoint:

- 10.1.1 Time to cognitive failure on any of the 6 primary variables from the pre-specified cognitive tests (HVLT-R total recall, HVLT-R delayed recall, HVLT-R delayed recognition, TMT Part A or Part B, COWA) with failure defined as a decline that meets or exceeds the reliable change index (RCI) for each cognitive test variable. A cumulative incidence approach will be used to estimate median time to cognitive failure in order to account for the competing risks of disease progression and death. Patients experiencing disease progression or patients that died prior to experiencing cognitive failure will be considered as having had a competing event. Progressive disease frequently causes cognitive decline, and the goal of this study is to assess the impact of the radiation treatment itself on cognitive decline.
- 10.2 Definitions of secondary endpoints:
 - 10.2.1 Local control and distant control in the brain will be measured by contrast-enhanced brain MRI scan using Response Assessment in Neuro-Oncology (RANO)Criteria, as follows [50].
 - 10.2.1.1 Complete Response (CR): Requires all of the following 1) complete disappearance of all enhancing measurable and non-measurable disease sustained for a minimum of 4 weeks; 2) no new lesions; 3) stable or improving nonenhancing (T2/FLAIR) lesions; 4) patients must be off corticosteroids (or on physiologic replacement doses only); and 5) stable or improved clinically.
 - 10.2.1.2 Partial Response (PR): Requires all of the following: 1) ≥50% decrease compared with baseline in the sum of products of perpendicular diameters of all measurable enhancing lesions sustained for at least 4 weeks; 2) no progression of non-measurable disease; 3) no new lesions; 4) stable or improved non-enhancing (T2/FLAIR) lesions on the same

or lower dose of corticosteroids compared with the baseline scan; 5) stable or improved clinically.

10.2.1.3 Progressive Disease (PD): Defined as any of the following 1) \geq 25% increase in the sum of the products of perpendicular diameters of enhancing lesions compared with the smallest tumor measurement obtained either at baseline (if no decrease) or best response, on stable or increasing dose of corticosteroids; 2) significant increase in T2/FLAIR nonenhancing lesion on stable or increasing doses of corticosteroids compared with baseline or best response not caused by comorbid events (i.e. radiation therapy. demvelination, ischemic injury postoperative changes); 3) any new lesion; 4) clear clinical deterioration not attributable to other causes apart from tumor (i.e. seizures, medication adverse effects, complications of therapy, cerebrovascular events, infection, or decrease in corticosteroid dose); 5) failure to return for evaluation due to death or deteriorating condition; 6) clear progression of non-measurable disease.

When making the diagnosis of progressive disease it is import to recognize the possibility of pseudo-progression, especially if the patient is clinically stable. In those situations, treatment should continue and status of local control should be evaluated with a repeat interval scan. If the subsequent scan confirms progression then the date of progression should be backdated to the original scan suggesting progression.

- 10.2.1.4 Stable Disease (SD): Requires all of the following 1) does not qualify for complete response, partial response, or progression; 2) stable FLAIR/T2 lesions on corticosteroid dose no greater than at baseline; 3) clinical status stable.
- 10.2.1.5 For local control, PD is considered local failure, or stable disease with deterioration of the neurological examination with a grade III or worse toxicity on the CTCAE v.4.0 scale (see Appendix). All others (CR, PR, asymptomatic SD) are deemed success.
- 10.2.2 Overall survival will be measured from registration until death. After 2 years of follow-up event monitoring will be used.
 - 10.2.2.1 Patients with unknown vital status will be censored at the date of last visit or MRI scan.
- 10.2.3 Quality of life will be measured at each two month interval follow up visit out to two years using the EORTC QLQ C30/BN20 and the MD Anderson Symptom Inventory Brain Tumor (MDASI-BT).
- 10.2.4 At each two month interval follow up visit out to 2 years all six prespecified cognitive test variables will be assessed. The pattern of cognitive change in memory, executive function, and processing speed will be assessed at each time point. The composite cognitive function

score will be determined by averaging standardized Z-scores from all pre-specified cognitive test variables (5 out of 6 are required to calculate a composite score).

- 10.2.5 MRI imaging including diffusion weighted images (DWI) and reconstructed apparent diffusion coefficient (ADC) maps will be analyzed for differences between pre- and post-treatment scans. They will also be analyzed for differences between the two treatment modalities.
- 10.2.6 Diffusion tensor imaging (DTI) will be analyzed for correlation to the cognitive changes and for differences between the two treatment modalities.
- 10.2.7 Pre-treatment factors of RPA class and MMSE will be assessed for predictive determination of local and distant control and cognitive outcome in each treatment arm.
- 10.2.8 Assessment will be made for correlation between location of primary lesion, total volume of intracranial disease, and cognitive outcome for each of the treatment arms.
- 10.2.9 The relationship between MGMT promoter methylation status and cognitive and local control outcomes will be assessed.
- 10.2.10 Post treatment side effects will be recorded at each follow up visit out to two years. Toxicity will be recorded according the Common Terminology Criteria for Adverse Events v4.0.3 for Nervous System Disorders. Only grade 3 and above toxicity that is directly related to therapy will be required to be documented. Pretreatment symptoms should not be considered as toxicity related to the treatment and are not required to be documented unless the symptoms worsen as a result of therapy.
- 10.2.11 Dosimetric parameters such as dose to the hippocampus will be analyzed for relationship with cognitive and local control outcomes.
- 10.3 Evaluation of correlative markers
 - 10.3.1 Genetic markers: DNA will be extracted within the first five fractions of treatment in the laboratory of the Study Chair. Apo E (i.e., Apo E2, Apo E3, and Apo E4) genes will be analyzed for single nucleotide polymorphisms (SNPs) either by Taqman or direct sequencing.
 - 10.3.2 Inflammatory Markers: Serum specimens collected within the first five fractions of treatment and at each follow-up visit will be analyzed using commercially-available ELISAs from R&D Systems, Inc. for the following inflammatory biomarkers: interleukin 1 (IL-1), interleukin 6 (IL-6), and tumor necrosis factor alpha (TNFα). These markers will be assayed in the laboratory of the Study Chair.
 - 10.3.3 Hormone and Growth Factors: Serum specimens collected within the first five fractions of treatment and at each follow-up visit will be analyzed using commercially available Enzyme Linked Immunosorbant Assays (ELISAs) for the following hormone and growth factors: glucocorticoids (e.g., cortisol), gonadal steroids (e.g.,

estradiol, testosterone, progesterone), growth hormone, human chorionic gonadotropin (hCG), insulin-like growth factor-1 (IGF-1), and neuronal growth factor (NGF). These assays will be performed in the laboratory of the Study Chair.

- 10.3.4 A portion of the serum and DNA will initially be analyzed as described above. According to patient consent information, the remaining body fluid biospecimens will be stored as de-identified frozen specimens in locked storage at -70°C in the laboratory of the Study Chair. As new protocols are developed they will be presented for IRB review and approval.
- 10.3.5 Return of Genetic Testing Research Results: Because the results generated by the genetic testing included in this section are not currently anticipated to have clinical relevance to the patient or their family members, the genetic results will not be disclosed to the patients or their physicians. If at any time, genetic results are obtained that may have clinical relevance, IRB review and approval will be sought regarding the most appropriate manner of disclosure and whether or not validation in a Food and Drug Administration (FDA) Clinical Laboratory Improvement Amendments (CLIA)-certified setting will be required. Sharing of research data with individual patients should only occur when data have been validated by multiple studies and testing has been done in CLIA-approved laboratories.
- 10.3.6 For analysis of MCP class, all assays will be performed on residual formalin-fixed, paraffin embedded (FFPE) tissue remaining after pathological diagnosis. Representative hemotoxylin and eosin sections will be used to identify tumor content by an M.D. Anderson Neuropathologist. FFPE-derived RNA and DNA will be prepared using the MasterPure Complete DNA and RNA purification kit (Epicentre Biotechnologies, Madison, WI) following deparaffinization using Citrisolve (Amity International, Anderson,SC). *MGMT* promotor methylation and G-CIMP status will be determined by bisulfite conversion of DNA and real-time PCR amplification. *IDH1* status will be determined from the medical record or by direct sequencing when necessary. 19-gene mRNA signature will be determined by real-time PCR following reverse transcription of mRNA

